## 11.3 Analysis Populations

There will be one analysis population in this trial:

- Safety population, defined as all patients who have received at least one dose of study treatment.

## 11.4 Descriptive Statistics

Categorical variables will be summarized with counts (n) and percentages (%). For continuous variables, the number of non-missing observations (n), mean, standard deviation (SD), standard error (SE) of the mean, 95% confidence interval (CI) of the mean, median, first (Q1) and third (Q3) quartiles, minimum (min) and maximum (max) will be tabulated. When applicable, these summaries will be provided by visit and time-point of assessment.

## 11.5 Demographics and Baseline Characteristics

Descriptive statistics will be used to summarize demographic and baseline characteristics.

## 11.6 Study and Treatment Compliance

Descriptive statistics will be used to summarize study and treatment compliance.

## 11.7 Prior and Concomitant Medications

The number and percentage of the patients with concomitant medications during the study will be summarized by anatomical therapeutic chemical class, standardized drug name.

## 11.8 Statistical Methods

The statistical approach for the analysis of safety and other endpoints is described below. A more detailed description of the statistical methods to be used will be provided in the SAP.

### 11.8.1 Analysis of Safety Endpoints

Descriptive statistics will be provided for all safety endpoints.

Local tolerability signs composite score, and specific local tolerability scores will be analyzed by means of descriptive statistics and provided by visit. The maximum local tolerability score and maximum local tolerability composite score will be presented. The number and percentage of patients with hypo- or hyperpigmentation and scarring in the TF will be presented separately by visit as well as the number and percentage of patients with change from baseline in hypo- or hyperpigmentation and scarring in the TF.

An AE will be considered to be a TEAE, if it was not present prior to the first dose of trial drug or was present prior to the first dose of trial drug but increased in severity after the date of the first dose of study treatment. An AE that occurs more than 57 days after the last IMP application will not be counted as a TEAE.

TEAEs and TESAEs recorded during the study will be presented, including the total number of events and the number and percentage of patients with events. Summaries of the number

and percentage of patients with TEAEs (and number and percentage of events), study drug-related TEAEs, TEAEs by severity, TESAEs, TESAEs with an outcome of death, and TEAEs leading to temporary or definite discontinuation of the study treatment will be provided. Specific tables describing AESIs will be also provided. The number and percentage of patients who experience one or more AESI will be tabulated by AESI.

For PEs, ECGs, vital signs, and clinical laboratory parameters, the number and percentage of patients with normal or abnormal results will be presented at scheduled visits. Descriptive statistics for continuous variables will be provided at scheduled visits together with a summary of changes from baseline for each parameter. Shift tables will be provided when appropriate.

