#### **8.4 Treatment Discontinuation Criteria**

Any patient may discontinue from study treatment at any time during the trial at the discretion of the Investigator or at the request of the patient. For patients who discontinue treatment, efforts should be made to encourage the patient to remain in the trial and complete the trial-related assessments. The main reason for such a premature treatment discontinuation must be documented in the electronic case report form (eCRF), as follows:

- Adverse event: If a patient experiences an AE, treatment discontinuation will be at the discretion of either the Investigator or the patient regardless of the causal relationship to the investigational medical product (IMP).
- Protocol deviation: Any protocol deviation detected should be corrected when possible and the patient should be allowed to continue. ONLY the following deviations should lead to treatment discontinuation: those which could affect patient's safety (eg, illness requiring treatment(s) which in the clinical judgement of the Investigator [or after discussion with the trial monitor] might invalidate the trial by interfering with the IMP) or which are due to patient unwillingness to comply with the trial activities or those violations of inclusion and/or exclusion criteria detected
- Lost to follow-up: Non-attendance. In these cases, every effort should be made by the Investigator to ascertain the reason and to assure patient's attendance as soon as possible. Every effort (at least three documented attempts) should be made to contact the patient and documented in the medical records. If patient cannot be reached after that, a registered mail letter will be sent to the patient and documented in the medical records
- Patient's personal request: The patient is permitted to stop his/her treatment at any time during the trial without incurring any loss in his/her medical care. The Investigator should ensure that such discontinuation is not due to an AE or disease exacerbation, in which case the corresponding reason should be recorded
- Pregnancy

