**Table 3 Local Tolerability Signs and Grading Scale**

Local Tolerability Signs	Local Tolerability Score
Erythema	0=absent
Flaking/scaling	1=mild (slightly, barely perceptible)
Crusting	2=moderate (distinct presence)
Swelling	3=severe (marked, intense)
Vesiculation/pustulation	
Erosion/ulceration	

Application site symptoms such as itching, burning, stinging, tenderness, pain etc., are not classified as local tolerability signs and will be reported as AEs.

All patients who have unresolved local tolerability signs in the TF at Day 57/ET will return for additional follow-up every 7 to 28 days until these have resolved, have returned to the baseline value, or are deemed stabilized by the Investigator.

Any sign of local tolerability leading to temporary or permanent discontinuation of the study drug application or requiring the use of concomitant medications should be reported as an AE. If a sign of local tolerability leads to an AE meeting the criteria of seriousness (ie, an SAE), the SAE form will be completed with all the available information and reported within the same timeframe and following the same routing as for an SAE (see Section 10.7.4).

In case of occurrence of possible contact dermatitis in the TF, an evaluation (patch test) will be made to confirm or rule out the diagnosis (see [Appendix 2](#)).

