‘Possibly related’ and ‘related’ will be considered as ‘related’ terms for reporting purposes. If the events are assessed as ‘unlikely related’ or ‘not related’ to the suspect IMP, the event does not qualify for reporting purposes. In the absence of information on causality from the reporting Investigator, the CRO will immediately contact the reporting Investigator to request a causality assessment. The case will be updated with the follow-up information and reported accordingly. If no causality is provided by the Investigator, the Sponsor assessment will be considered for submission purposes.

- The outcome of the event will be described in terms of:
  - Recovered/resolved
  - Recovering/resolving
  - Recovered/resolved with sequelae
  - Not recovered/not resolved
  - Fatal
  - Unknown
- The action taken on the IMP will be captured as:
  - Drug withdrawn
  - Dose not changed
  - Not applicable

An AE will be collected only once with its maximum severity, except when the AE started before first IMP administration and persisted after it and worsened in severity any time after first IMP application. In this latter case, the AE will be collected with each respective severity. The AE term recorded must be exactly the same at the different time points where this AE is reported again in the eCRF.

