### 14.2 Patient Information and Informed Consent

Patients will be informed by the Investigator in detail of the characteristics of the drug to be administered, the nature of the clinical investigation, the risks and the discomfort that can reasonably be expected as a result of their participation and the uses of the data, as described in the Patient Information Sheet (PIS).

The patients will be informed that they are free to withdraw their consent and suspend their participation in the trial at any time with no penalty or loss of benefits to which the patient is otherwise entitled. Administration of the drug may be interrupted, and a patient withdrawn from the trial at the discretion of the Investigator. The Investigator should justify his decision in the patient's eCRF.

Any patient considered by the Investigator to be suitable for inclusion must document his or her willingness to participate in the trial by giving his or her informed consent in writing before starting any trial procedure by signing the ICF, which must be signed and dated by the patient and the Investigator. Explicit consent to participate in the standardized photography procedure will also have to be given by patient.

At such time the patient must be given adequate time to understand the information provided and ask questions, if required. Any new relevant information that becomes available during the trial will be provided to the patient.

The PIS and ICF will include all elements required according to the applicable legislation. These documents or any modification will have been authorized by Almirall, S.A. and approved by the relevant IRB/IEC before use.

Patients will have access to the written PIS and ICF in paper or electronic format, preferably but not exclusively through a web system (eConsent). When using the eConsent process, the system will allow for on-line meetings between the patient and Investigator to facilitate answering patient questions and recording the responses. Patients will give their consent by signing electronically the ICF (eConsent). Patients will be requested to download the signed ICF, and/or ask the Investigator for a printed version. While they are in the study, patients will always have access to the PIS and ICF through eConsent. When eConsent cannot be used, the patient will sign a paper ICF.

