## Appendix 2, Patch Test for the Assessment of Contact Dermatitis

In the event the patient experiences a skin reaction of such nature or severity that an allergic contact dermatitis is suspected, the patient can be treated with topical treatment with corticosteroids (eg, betamethasone) and oral antihistamines and should temporally discontinue the study medication. The event should be documented as an adverse event and the medication given recorded. The patient should be re-challenged using the assigned study medication (patch test in the back) to confirm or rule out contact dermatitis. If the diagnosis of allergic contact dermatitis is confirmed the patient may have an additional patch test with both the tirbanibulin-containing ointment and the vehicle base.

The patch test will be performed at least 2 weeks after last treatment or discontinuation of the study medication. Patches will be applied to untreated areas on the back for 48 hours. Readings will be performed approximately 15 to 30 minutes and 48 hours following the removal of the patches. At the investigator's discretion, a facultative additional reading might be performed at 96 or 120 hours after removal of the patches if an equivocal reaction is observed at the previous reading. If allergic contact dermatitis is confirmed the patient will discontinue permanently the study medication, on the contrary the patient can be treated with the study medication if necessary.

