14.3 Adverse Events

AEs will be coded according to the MedDRA, Version 25.0.

TEAEs will be defined as any AEs with onset date/time on or after the first study treatment dosing and prior to the last date of study treatment dosing + 57 days (inclusive), or as any AE that was present prior to the first dose of trial drug but increased in severity on or after the first study treatment dosing and prior to the last date of study treatment dosing + 57 days (inclusive). AEs starting on the first study treatment dosing date and related to a pre-dose study assessment will not be considered as TEAE. See Appendix 2 for handling of completely or partially missing dates and time for AEs. In the case where it is not possible to define an AE as treatment emergent or not, the AE will be classified as treatment emergent.

Overall summaries of AEs will be presented by number and percentages of patients with and number of events of AEs, TEAEs, study treatment-related TEAEs, TESAEs, TEAEs by worst severity, TEAEs leading to study treatment discontinuation, TEAEs leading to study discontinuation, application site TEAEs, AESIs, and TEAEs with an outcome of death.

Frequency and percentage of patients who experience TEAE will be summarized by SOC and PT within SOC. Unless otherwise specified, a patient experiencing the same TEAE multiple times will be counted only once for the corresponding PT. Similarly, if a patient experiences multiple TEAEs within the same SOC, the patient will be counted only once for that SOC. TEAEs will be sorted alphabetically by SOC and within each SOC the PT will be presented by decreasing order. Treatment-emergent SAEs, TEAEs leading to study treatment discontinuation, TEAEs with an outcome of death and TEAEs leading to study discontinuation will be summarized similarly.

Frequency and percentage of patients who experience TEAE will also be summarized by SOC, PT and worst severity (mild/moderate/severe). TEAE with an unknown severity will be considered as severe. If a patient experiences more than one TEAE within different severity categories within the same SOC/PT, the patient will be counted only once under each SOC/PT under the worst severity.

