16 CHANGES TO ANALYSES SPECIFIED IN THE PROTOCOL

The changes made to analyses specified in the protocol are presented in [Table 3](#).

Table 3 [Changes to Analyses Specified in the Protocol](#)

Description of the Change	Rationale

Protocol states that Unscheduled tests will not be associated with any trial visit. However assessments performed at each study visit will be remapped based on windowing conventions specified in Section 7.3.
	
To minimize missing data in table reporting.

Protocol states that the number and percentage of patients who experience one or more AESI will be tabulated by AESI. However the number and percentage of patients who experience one or more AESI will rather be tabulated by SOC and PT.
	
The only type of AESI considered in this study is skin cancer.

M-14867-32

Statistical Analysis Plan Status: Version (17 Jan 2023)

Protocol states the number and percentages of patients with events, and number and percentage of events will be presented for TEAEs.	Only the number and percentages of patients with events, and the number of events will be reported. Percentages of events will not be reported.
Protocol states subgroup analyses for exploratory endpoints only.	Exposure, compliance and local tolerability assessments will also be provided by subgroup of treatment area (face/scalp).

M-14867-32

Statistical Analysis Plan Status: Version (17 Jan 2023)

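### The AE action-taken field has no value for a temporary stop, although the protocol plans to summarize TEAEs leading to one, and SAP 14.3 leaves the scope of that summary undefined

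*Protocol*

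**What the plan says.** **Planned output.** Among the safety summaries, protocol 11.8.1 (version 2.0) states that "TEAEs leading to temporary or definite discontinuation of the study treatment will be provided". The synopsis says the same. This is one pooled summary: temporary and definite stops count together.

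**Temporary stops are foreseen.** Protocol 10.5.2.1, in the text under the grading table, requires an AE report for any local tolerability sign "leading to temporary or permanent discontinuation of the study drug application". Appendix 2 says that a patient with suspected allergic contact dermatitis "should temporally discontinue the study medication", and that the event is to be documented as an AE.

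**Data field.** Protocol 10.7.2 introduces a list with "The action taken on the IMP will be captured as" and gives three values: *Drug withdrawn*, *Dose not changed* and *Not applicable*.

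**SAP.** The overall AE summary in SAP 14.3 includes "TEAEs leading to study treatment discontinuation, TEAEs leading to study discontinuation, application site TEAEs". No qualifier says temporary or permanent, and no source variable is named. SAP section 16 opens with "The changes made to analyses specified in the protocol are presented in" and points to its Table 3. The four entries there concern unscheduled assessments, AESI tabulation, percentages of events, and subgroups.

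**Other records of a pause.** Protocol 9.5 has treatment delays entered in the diary and dosing deviations in the eCRF. The January 2023 clarification letter accepts a paper diary as a source too. SAP 11.2 plans a listing that includes drug interruption, and SAP 14.3 lists all AEs.

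**The concern.** The primary objective is safety and tolerability. In a 5-day course, a pause because of an adverse event is a direct sign of poor tolerability, and the protocol explicitly promises to count such events. The field that would normally define the count offers no value that describes a pause, so the investigator must choose one that misdescribes it. The documents do not say which.

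The SAP then carries the output forward under a shorter label. Under SAP 3.1 the SAP governs where it differs from the protocol, so its wording decides what the table contains. A reader of the finished row could not tell whether it covers pauses. Even a zero would be hard to interpret, because it could mean that no pauses occurred, that pauses were coded under another value, or that pauses were outside the definition.

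**Working it through.** No figure in the plan needs reproducing, and the documents give no interruption rate. The check sets the passages side by side.

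**Step 1: what the summary needs.** Protocol 11.8.1 needs every TEAE that led to a temporary or a definite stop to be identifiable. It does not need the two kinds to be told apart.

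**Step 2: what the field gives for a pause.**

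| Value chosen for a pause | Does it describe the pause? | Effect on a pooled summary taken from *Drug withdrawn* |
|---|---|---|
| *Drug withdrawn* | No, if dosing resumed | Counted |
| *Dose not changed* | No | Missed |
| *Not applicable* | No | Missed |

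One of the three choices feeds the pooled summary and two do not. Protocol 10.7.2 gives no instruction on which to use, so the count can depend on site habit.

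**Step 3: what the SAP adds.** SAP 14.3 could resolve this by naming a source variable or by stating that pauses count. It does neither. Two readings remain open: discontinuation as the umbrella word, or permanent stops only. SAP Table 3 declares no change, which is compatible with the first reading but does not state it.

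**Step 4: whether other records close the gap.** In both foreseen situations an AE record exists for the causing event, because protocol 10.5.2.1 and Appendix 2 require it. The pause itself appears in the diary, the dosing-deviation records and the SAP 11.2 listing. A reviewer could match these by hand. Neither document plans a step that turns the match into the summary in 11.8.1.

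**Step 5: size.** Protocol 8.1 plans about 100 treated patients, and SAP Appendix 1 makes the population count the default denominator. Each patient with a missed AE-driven pause lowers the reported percentage by 1/100 = 1 percentage point. If no patient stopped permanently and one pause was coded as *Dose not changed*, the row would read 0/100 = 0% instead of 1/100 = 1%. This shows the effect of one case and does not predict how many will occur.

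**The case against.** The best defence has four parts.

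**The field can still supply the summary.** A reader might infer that the three values make the summary in 11.8.1 impossible. The documents do not support that. The summary is pooled, so a pause coded as *Drug withdrawn* is counted correctly in it. What stands is narrower: nothing directs sites to that value, and it is inaccurate when dosing resumes.

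**The SAP may simply mean both.** A reader might infer that the SAP dropped temporary stops. That does not follow either. The protocol uses discontinuation as the general word and qualifies it when needed, and SAP Table 3 declares changes as small as omitting percentages of events. Its silence is fair evidence that nothing was meant to change. What stands is that this reading has to be inferred.

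**Pauses are not lost.** A reader might infer that a pause cannot be connected to its cause. That is too strong, given the required AE records and the listings described above. Tracing single cases by hand is realistic in about 100 patients.

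**Few events are likely.** In the earlier 100 cm² trial, composite scores peaked around Day 7 to 8, after the last planned dose (protocol 5.1.5). The pivotal trials had no discontinuations due to a TEAE (protocol 5.2). This limits the consequence without removing the mismatch.

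The sentence on interruption in protocol 14.2 should not be used as further evidence. It joins interruption to withdrawal from the trial and sits in the consent section.

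**Conclusion.** The point holds and is minor. The protocol plans to count AE-driven temporary stops and requires AE records for them, but its closed list of action-taken values has no correct entry for one. Following the list as written can therefore give an incomplete count. SAP 14.3 leaves the scope and source of the corresponding summary unstated.

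The conclusion rests on two assumptions: that the eCRF uses the three values in protocol 10.7.2, and that the summary is programmed from that field. The eCRF was not available. If it holds a further field tying an interruption to an AE, the data-capture part falls away and only the definition in SAP 14.3 remains. The effect is confined to one descriptive safety summary, at about 1 percentage point per misfiled patient.

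**What to change.** 1. Reconcile the action-taken list in protocol 10.7.2 with 10.5.2.1, 11.8.1 and Appendix 2 by adding a *Drug interrupted* value.
2. If the eCRF is frozen, issue a query before database lock for each recorded interruption, asking the investigator whether it was due to an AE and which one. The diary (app or paper) and the dosing-deviation records identify the cases. Cause should not be inferred from dates alone.
3. In SAP 14.3, state that the treatment-discontinuation summary covers temporary and permanent stops, and name the variable that defines it. If only permanent stops are wanted, declare and justify that in SAP Table 3.

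Separate rows for temporary and permanent stops would be informative but are optional, since protocol 11.8.1 asks only for the pooled summary.

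The cost is one pick-list value or a small number of queries, plus a sentence in the SAP. No visits or assessments are added, and no treatment rule changes.

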## **11.8.2 Analysis of Exploratory Endpoints**

Descriptive statistics will be provided for exploratory endpoints overall and by subgroup (see Section 11.11). An Observed Cases approach will be used for handling missing data, as the main analysis (see Section 11.9). Any other sensitivity analyses will be defined in the SAP.

## **11.9 Handling of Missing Data**

No imputation will be made for missing data.

